Water, Sanitation, and Hygiene Mobile Health Messages as an Innovative Tool to Facilitate Behavior Change

NCT04816552

January 27, 2020

JHSPH IRB Research Plan for New Data Collection

PI Name: [name]

Study Title: Water, Sanitation, and Hygiene Mobile Health Messages as an Innovative Tool to Facilitate

Behavior Change

IRB No.: IRB00009255

PI Version No. / Date: Version 5 / January 27, 2020

I. Aims of the Study: Describe the aims/objectives of the research and/or the project's research questions or hypotheses.

Aim 1. Develop an evidence and theory based WASH mHealth intervention for households in areas with confirmed cholera patients in Dhaka, Bangladesh through formative research

- a. Conduct formative research through in-depth interviews, focus group discussions, and intervention planning workshops with caregivers and household members of young children, and government officials to identify perceptions of WASH behaviors and to inform the development of intervention materials.
- b. Pilot the WASH mHealth intervention in a subset of households, and revise according to feedback.

Aim 2: Evaluate the effectiveness of the developed WASH mHealth intervention in increasing WASH behaviors and reducing fecal contamination on hands and in stored drinking water by conducting a RCT

- a. Recruit and prospectively follow for 12 months 300 households (1200 participants, 4 per household) with a child under five years of age assigned to one of two study arms (150 households per arm). The first arm will receive the CHoBI7 mHealth program (CHoBI7 mHealth program Arm) and the second arm will serve as a Control Arm and only receive a general message on oral rehydration solution (ORS).
- b. Compare the 2 study arms using structured observation of handwashing with soap at stool and food related events, unannounced spot checks of the presence of soap in the cooking and latrine areas of the household, and fecal coliform counts on caregiver hands and in stored drinking water.
- **II.** Background and Rationale: Explain why this study is being done. Summarize briefly what is already known about the issue and reference previously published research, if relevant.

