After developing the new mHealth modules we will conduct a pilot study to assess the uptake of the intervention. The sample size for the pilot will be 300 participants (~75 households) (60 standard ORS message participants and 240 WASH mHealth participants). The in-depth interviews, focus group discussions, and intervention planning workshops will be conducted in parallel with the pilot. This combined approach will allow us to learn about the effectiveness of our messages in terms of the uptake of the promoted WASH behaviors (through spot checks and structured observation) and participant and stakeholder perceptions around the developed messages (qualitative activities). The pilot study will be conducted using an iterative process where we will have 3 phases. During each phase approximately 80 participants (~20 intervention households) will be given our developed mHealth messages, and 20 participants (~5 households) will receive only the standard message on the use of ORS for dehydration. mHealth messages will be refined and expanded throughout the pilot as we learn more about the effectiveness of our messages in terms of the uptake of the promoted WASH behaviors and participant perceptions of messages. Each household will be followed for a duration of 3 months to investigate sustained WASH practices over time.

Intervention Evaluation

Our objective is to first establish if the intervention can improve our behavioral outcomes and fecal contamination in the household. The primary outcomes are: (1) handwashing with soap at stool and food related events during structured observation, (2) fecal coliform counts on hands and in stored drinking water, and (3) the presence of soap in cooking and latrine areas (within 10 steps) during unannounced spot checks.

Psychosocial factors potentially related to WASH behavior will be measured using a Likert-scale questionnaire at baseline and 1 week, and at the 1, 6, and 12 month follow-up.[2]

Five-hour structured observation will be conducted at baseline, 1 week, and 1 month (habit formation), and 3, 6, 9, and 12 (habit maintenance) months after enrollment to observe handwashing with soap at the following food and stool related events: (1) after using the toilet; (2) after cleaning a child's anus; (3) before eating; (4) before feeding a child; and (5) before preparing food (see our recent publications). [3, 4]

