Unannounced spot check visits will be conducted at baseline, 1 week, and 1 month (habit formation), and 3, 6, 9, and 12 (habit maintenance) months after enrollment in households to observe: (1) the presence of soap in the latrine and cooking areas of the household (within 10 steps); and (2) measure fecal coliform counts in stored drinking water and on hands.

Clinical Surveillance. Participants will be asked questions about their health (e.g. diarrhea, vomiting), and if they have visited a health provider for care or have taken medication (e.g. antibiotics) at baseline, 1 week, and monthly thereafter for the 12 month study period. Participants will also be asked about their intervention exposure (e.g. visits and mobile messages received). Child height and weight will be measured at baseline, and 6 and 12 months.

Power Calculation and Statistical Analysis. Our sample size of 300 households is based on the largest number of households we could recruit based our budget. Our power calculation is summarized in Table 2 below. We will compare demographic and socioeconomic factors between arms to determine whether randomization was successful in defining similar groups of households. We will conduct linear regression models for continuous variables and logistic regression models for binary outcomes to compare intervention arms at specific follow-up times. The predictors in these models will be study arm. Generalized estimating equations will be used for individual level variables to account for clustering in the household, as well as comparing the rate of change over time within households. To investigate potential psychosocial factors mediating the intervention effect, mediation models will be performed using the "INDIRECT" macro. [2, 5] All analyses will be performed using SAS 9.3.

Table 2. Power calculation. Detectable differences for outcomes between intervention and comparison arm for 80% power, assuming 10% loss to follow-up among 300 enrolled households resulting in 270 households at the 12 month follow-up

Outcomes	N	Anticipated % in Control Arm (Based on Current Trial)	Detectable Difference Between Intervention and Control Arms
% Individuals handwashing with soap at a stool or food related event during structured observation (100 randomly selected households per timepoint (400 participants at each visit with 10% loss to follow-up))*	360	25%	16%
% Households with soap present in cooking area at a spot check	270	31%	17%

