% Households with soap present in latrine area at a spot check	270	51%	17%
% Household with stored drinking water <1 CFU/100 MI E.coli (100 randomly selected households per timepoint)	90	8%	23%
% of Hand rinses samples with detectable fecal coliforms (100 randomly selected households per timepoint with 10% loss to follow-up)	90	90%*	24%

^{*}Assuming an intra-class correlation of 0.1 for handwashing with soap of individuals in the same household, for a design effect of 1.3.

- B. Provide a sample size and a justification as to how you arrived at that number. If you use screening procedures to arrive at a final sample a table may be helpful.
- In-Depth Interviews (30-40 Participants): We will conduct in-depth interviews with key audience segments to identify appropriate mHealth messages, including households living in areas identified to have cholera patients, health facility staff and directors, and government officials.
- Focus Group Discussions (60-80 Participants, 6-12 participants per group): We will conduct focus group discussions with the same segments of key stakeholders as the in-depth interviews to identify appropriate WASH intervention messages.
- Intervention Planning Workshops (45-60 participants): These workshops will be held with government officials and health providers to review mHealth messages, and to discussion integration of these messages into the national program for cholera outbreaks.
- Pilot Study (300 Participants (75 households, approximately 4 participants/household)): We will recruit 300 participants (~75 households) for a pilot study of developed mHealth messages. We will follow these households prospectively for up to three months to observe the uptake of the promoted behaviors. Modifications of intervention and study tools will be made according to feedback from pilot study participants.

Randomized Controlled Trial (1200 Participants (300 households, approximately 4

participants/household)): We will recruit 1200 participants (300 households) for a randomized controlled trial of the developed mHealth messages. We will follow these households prospectively for up to twelve months to observe the uptake of the promoted behaviors.

IV. Participants:

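### Does the handwashing outcome lack a fixed unit, so that the 16-point detectable difference in Table 2 cannot be relied on?

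*Combined protocol and SAP*

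**What the plan says.** Section I, Aim 2b: "Compare the 2 study arms using structured observation of handwashing with soap at stool and food related events". The primary outcome list in section III.A (Intervention Evaluation) uses the same idea: "1) handwashing with soap at stool and food related events during structured observation". Neither gives a numerator, a denominator or a unit. The observation lasts five hours and covers five event types: after toilet use, after cleaning a child, and "3) before eating; (4) before feeding a child; and (5) before preparing food". Two publications are cited beside that list.

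Table 2 is the one place that names a unit: the percentage of "Individuals handwashing with soap at a stool or food related event during structured observation". Its N is built from people, "100 randomly selected households per timepoint (400 participants at each visit with 10% loss to follow-up", which gives 360. Its footnote reads "Assuming an intra-class correlation of 0.1 for handwashing with soap of individuals in the same household, for a design effect of 1.3". The control figure of 25% stands under the column heading "Anticipated % in Control Arm (Based on Current Trial", with no further account of how it was obtained.

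The analysis paragraph gives logistic regression for binary outcomes at specific follow-up times and adds: "Generalized estimating equations will be used for individual level variables to account for clustering in the household".

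**The concern.** Within five hours one person may eat, prepare food and use the toilet, and so have several events. An infant, whom the enrolment rules allow, may have none. If the wording about events is taken to make the event the unit, it seems to conflict with the count of individuals in Table 2. Even if the person is the unit, two rules are missing: how mixed behaviour over several events becomes one value, and whether a person with no event counts as not washing or leaves the denominator.

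This is the first-listed primary outcome. If unit, scoring and denominator were truly open, they could be chosen after the data were seen, and the same records could yield arm differences of different size. The 16 points would then describe only one of several possible analyses.

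**Working it through.** **1. The plan's own figure.** Inputs from Table 2 and its footnote: 360 people, so 180 per arm; control 25%; intervention 25 + 16 = 41%; ICC 0.1 with four people per household; 80% power. Two-sided 5% is my assumption, since no alpha is stated.

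- Design effect: 1 + (4 − 1) × 0.1 = 1.3. Effective number per arm: 180 / 1.3 = 138.5.
- Required per arm: n = [1.960 √(2p̄(1 − p̄)) + 0.842 √(p₁(1 − p₁) + p₂(1 − p₂))]² / d². With p̄ = 0.33 and d = 0.16 this is (1.960 × 0.665 + 0.842 × 0.655)² / 0.0256 = 134.4, rounded up to 135.
- Total with clustering: 2 × 135 × 1.3 = 351, against 360 available.
- Solving for d at 138.5 per arm gives 15.75 points, which rounds to the stated 16. Power at 16 points is 81.2%.

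The row reproduces as a person-level calculation in which each of the 360 people gives one binary value.

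**2. Do the passages conflict?** Aim 2b and the outcome list say on which occasions handwashing is watched; they do not say what is counted. Four places give or imply a unit, and all point to the person: the Table 2 label, its N, the ICC between individuals, and the GEE sentence. The singular event in the Table 2 label reads most naturally as washing at one or more events, which largely settles the case of several events. The person with no event is not covered.

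**3. What other readings would do.** Events per person (k), the share of people seen at an event, and the within-person correlation (ρ) are assumptions; the documents give none of them.

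*(a) Same behaviour counted per event.* Suppose 25% v 41% of people wash at least once. With two events, P(at least once) = 1 − (1 − p)² − ρp(1 − p); for three events I used the corresponding beta-binomial. Solve for p in each arm. The variance factor is 1 + (k − 1)ρ + 3k × 0.1, and the effective number per arm is 180k divided by that factor.

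| k | ρ | Per-event rates | Difference | Variance factor | Effective n per arm | Power |
|---|---|---|---|---|---|---|
| 2 | 0.1 | 14.1% v 24.4% | 10.3 | 1.7 | 211.8 | 77% |
| 2 | 0.3 | 15.7% v 27.2% | 11.4 | 1.9 | 189.5 | 78% |
| 2 | 0.5 | 17.7% v 30.4% | 12.7 | 2.1 | 171.4 | 79% |
| 3 | 0.1 to 0.5 | – | 7.7 to 11.1 | 2.1 to 2.9 | 257.1 to 186.2 | 71% to 76% |

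The difference shrinks, but more records and rates further from 50% offset most of that. The fall from 16 to about 10 points is chiefly a change of scale.

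*(b) The event is the unit and 25% is a per-event rate.* The detectable difference is 12.6 to 14.1 points for two events and 11.4 to 13.5 for three, which is better than the stated row.

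*(c) Only people with an event are analysed, 90 households.* With 3.5 such people per household the design effect is 1.25 and n per arm is 157.5 / 1.25 = 126, so the detectable difference is 16.6 points. With three it is 1.2 and 135 / 1.2 = 112.5, giving 17.6 points.

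*(d) No event counted as not washing, with 25% taken to exclude such people.* If 87.5% are seen at an event, the rates are 21.9% v 35.9% and power is 73%. If 75% are seen, they are 18.75% v 30.75% and power is 64%. If the 25% already counts such people as not washing, the rates are 25% v 41% of all persons and the 81% of step 1 returns.

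*(e) One event per person.* All readings coincide and 16 stands.

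**The case for a change.** The strongest case is that a primary outcome should be fixed in the plan itself. Accepting the person as the unit does not supply the rule for someone with no event, and with no lower age limit such people are likely. The basis of the 25% is unstated: if it is a per-event rate, the share of control people washing at least once would be 34% to 42% with two events per person (ρ from 0.5 to 0.1). The cited publications may define the outcome, but the plan does not say that it adopts their definition. Two or three sentences would close the gap at no cost in households or visits.

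The factual part stands: the rule for people with no event and the basis of the 25% are not written down, and an analyst must supply the first. The inference to a defect does not. The largest power loss, in (d), needs the trial to count people differently from the source of the 25%, and nothing in the documents says that it would. The worry that a per-event difference of 10 points would be judged against 16 also carries little weight, because a result is judged by its estimate and interval and not by a planning difference. Finally, the case does not show that one definition is better than another; it asks only that one be recorded.

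**Conclusion.** No change follows. The plan points to a person-level outcome, and on that reading the 16 points are right (15.75 recomputed, two-sided 5% assumed). Other readings move the detectable difference to either side of 16, from about 11.4 to 17.6 points, and only through assumed inputs, so no stated figure or rule is shown to be wrong. The number of households was set by budget and would not move.

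The remaining gap is one of detail. An analyst may score a person as having washed at one or more events and leave out those with no event, or may model events with GEE clustered on household. Either gives a valid arm comparison, because clustering on household also covers repeated events within a person. Leaving out people with no event is harmless provided that the intervention does not alter who is seen eating, feeding, cooking or using the toilet, which is reasonable for a handwashing message but is an assumption. What stays open is some freedom in the exact definition; it concerns reporting, and does not make the design or the sample size unsound.

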Describe the study participants and the population from which they will be drawn. Specify the inclusion and exclusion criteria. If you plan to include children, note their ages and whether you will include children in foster care. Note if the participants are particularly vulnerable in terms of cognitive limitations, education, legal migration status, incarceration, poverty, or some combination of factors.

Participants will include households living in areas identified to have cholera patients, government officials in Bangladeshi Ministry of Health and Family Welfare, and health facility staff and directors. Study participants will be recruited from Dhaka, Bangladesh. The majority of the study population will be Asian, but that is not an inclusion/exclusion criteria. Children living in households will be included in the pilot of the developed intervention approaches. There is no age restriction for enrollment into the pilot trial or randomized controlled trial newborn or older). For the In-Depth Interviews and the Focus Group Discussions we will include only participants that are 12 years of age and older. For the Intervention Planning workshops we will only include adults 18 years of age or older.

Individuals under 18 years of age who are married or otherwise considered "emancipated" will complete the consent form and if not considered "emancipated", a parent may complete the Parental Permission Form.

Inclusion Criteria:

Eligibility Criteria

- In-depth Interviews and focus group discussions will include households living in areas identified to have cholera patients, health facility staff and directors, and government officials. In-depth interview and focus group discussion participants living in areas with identified cholera patients must have: (1) at least one household member reporting ownership of an active mobile phone in their possession on the day of enrollment; and (2) must also have a child under 5 years of age in their household.
- **Intervention planning workshops** will include government officials in the Bangladeshi Ministry of Health and Family Welfare and health facility staff and directors.
- **Pilot households** must have: (1) at least one household member reporting ownership of an active mobile phone in their possession on the day of enrollment; (2) must also have a child under 5 years of age in their household; and (3) must plan to reside in their household for the next three months.

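### Does the handwashing row of Table 2 overstate power by counting all four enrolled members of each household as scored?

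*Combined protocol and SAP*

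**What the plan says.** Handwashing with soap at stool- and food-related events is the first-listed primary outcome (section III.A, Intervention Evaluation). It is measured by direct observation: "Five-hour structured observation will be conducted at baseline, 1 week, and 1 month (habit formation", and again at 3, 6, 9 and 12 months. Five event types count: after toilet use, after cleaning a child, before eating, before feeding a child, and before preparing food.

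The handwashing row of Table 2 takes the percentage of individuals as its outcome and is based on "100 randomly selected households per timepoint (400 participants at each visit with 10% loss to follow-up". It gives N=360, 25% in the control arm (attributed to a current trial) and a detectable difference of 16 points. The footnote reads "Assuming an intra-class correlation of 0.1 for handwashing with soap of individuals in the same household, for a design effect of 1.3". The heading of the table applies attrition to households, "assuming 10% loss to follow-up among 300 enrolled households resulting in 270 households at the 12 month follow-up", and the hand-rinse row (N=90) does the same: "100 randomly selected households per timepoint with 10% loss to follow-up".

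Aim 2a enrols "300 households (1200 participants, 4 per household) with a child under five years of age". Section IV adds "There is no age restriction for enrollment into the pilot trial or randomized controlled trial newborn or older". For the analysis, "Generalized estimating equations will be used for individual level variables to account for clustering in the household". Section III.A also states that the 300 households are the most the budget allows.

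**The concern.** A person can be scored for handwashing only if a qualifying event is seen during the session. Three of the five event types arise only for someone who looks after a child or cooks. Every household has a child under five, and newborns may be enrolled, so some enrolled members may have no event in five hours. The row makes no visible allowance for this. The 10% looks fully used by household loss, and the design effect covers clustering, not missing scores.

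The plan also does not say whether a member without an event is left out or counted as not washing, or which of these lies behind the 25%. If such members are left out, the number analysed is below 360 and the detectable difference is larger than printed. This row is the only power statement for the outcome. An open denominator also leaves room to choose it after the data are seen.

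**Working it through.** **Inputs from the documents:** 100 households per timepoint, 4 members each, 10% loss, ICC 0.1, control rate 25%, 80% power, and 1:1 allocation (150 households per arm in Aim 2a).

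**Assumptions:** a two-sided 5% test and pooled variance (the plan states neither), and an equal split of the observed households, 45 per arm.

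**Step 1. Rebuild the row.**

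- N = 100 × 4 × 0.90 = 360.
- Design effect = 1 + (4 − 1) × 0.1 = 1.3, so the cluster size used is four.
- Effective n per arm = 180 / 1.3 = 138.5.
- For a difference d, with p1 = 0.25, p2 = p1 + d and p̄ their mean, n per arm = [1.96 √(2p̄(1 − p̄)) + 0.842 √(p1(1 − p1) + p2(1 − p2))]² / d².
- Solving for n = 138.5 gives d = 15.75 points (printed: 16). Power for 25% against 41% is 81%.

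The same formula gives 16.58, 16.68, 23.12 and 24.18 points for the other four rows (printed: 17, 17, 23 and 24). All five match, which supports the assumed test. One-sided 5% gives 13.88 for handwashing and does not match.

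**Step 2. Let fewer members be scored.** With m members scored per household, n per arm = 45m / (1 + (m − 1) × 0.1). The documents give no value of m below 4, so these values are illustrative.

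| m scored | N | Design effect | n per arm | Detectable difference | Power for 16 points |
|---|---|---|---|---|---|
| 4 | 360 | 1.300 | 138.5 | 15.75 | 81% |
| 3.75 | 337.5 | 1.275 | 132.4 | 16.13 | 79% |
| 3.5 | 315 | 1.250 | 126.0 | 16.55 | 77% |
| 3 | 270 | 1.200 | 112.5 | 17.58 | 73% |
| 2 | 180 | 1.100 | 81.8 | 20.80 | 59% |

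Losing a member lowers the design effect as well as N, which softens the loss. The figure still rounds to 16 down to m = 3.53, that is 3.53 / 4 = 88% of members.

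**Step 3. Compare with the uncertainty already in the row.** With all four members scored, ICC 0.05 gives 14.76 points and ICC 0.20 gives 17.58. The upper value equals that for m = 3 at ICC 0.1, because both give 112.5 per arm (180 / 1.6 and 135 / 1.2).

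**Step 4. Test the other fixed inputs.**

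- At ICC 0.05, a printed 16 holds down to m = 3.12 (78%).
- The plan does not say whether the 100 households are drawn before or after loss. If they are drawn from those still in follow-up (about 270 at 12 months), there are 50 per arm. At ICC 0.1 the differences are then 14.9 (m = 4), 15.7 (m = 3.5) and 16.6 points (m = 3), and 16 holds down to m = 3.06 (76%).
- If the 25% was calculated over all enrolled members, and the analysis does the same, N stays at 360 and the row stands.

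**The case for a change.** The strongest case for acting is about the denominator. Leaving out members without an event and counting them as not washing give different estimands for a primary outcome, and a stated rule would close off a choice made with the data in hand. The loss could also exceed a point or two: with only two of four members scored, the row would read 20.8 points, and power for 16 would be 59%. The pilot uses structured observation and might show the share scored.

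Part of this stands: the denominator is not written down, and one sentence would have settled it. The rest is weaker. No document gives a share as low as one half, and two of the five event types, toilet use and eating, can apply to most members. The pilot text does not say that its sessions last five hours or record events by member. The documents also do not settle which denominator is right. The primary outcome is worded by events, the power row by individuals, and a denominator of members with an event conditions on something seen after randomisation. A reviewer who prescribed one would be making the sponsor's choice. Finally, the observation method and the 25% are referred to earlier work that is not reproduced in the plan, so the scoring convention may be set there.

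**Conclusion.** The concern is right about how the row was built and right that the denominator is not stated. It does not show that 16 points is wrong. The row reproduces at 15.75 points under an assumed two-sided 5% pooled test. An assumed 3 to 3.5 members scored (90 households, ICC 0.1) would move it to between 17.6 and 16.6 points, within the 14.8 to 17.6 that ICC 0.05 to 0.20 gives with all four scored. Under other plausible readings (a lower ICC, 100 retained households observed, or a 25% that covers all enrolled members), 16 survives further loss of scored members or needs no adjustment.

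No design decision depends on the answer, because the budget fixes 300 households and the table only describes what one visit can detect. Individual-level generalised estimating equations that account for household clustering give a sound comparison of randomised arms if one denominator is applied to both. This is missing detail that analysts would fill sensibly. The conclusion would weaken if far fewer than three members per household were scored, but nothing in the documents indicates that.

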- Randomized Controlled Trial participants must have: (1) at least one household member reporting ownership of an active mobile phone in their possession on the day of enrollment; (2) must also have a child under 5 years of age in their household; (3) must live in an area identified to have cholera patients by the icddr,b surveillance system; and (4) must plan to reside in their household for the next 12 months

• Exclusion Criteria:

Children in foster care will be excluded from all research study activities. If the interviewer becomes aware when talking to an adult respondent (18 years or older) that they appear to have a cognitive limitation, an adult household member may sign the Consent form on their behalf.

No one will be excluded because of age, sex, religion, or sexual preference.

Children younger than 12 years of age will be excluded from the in-depth interviews, focus group discussions, and workshops. Children younger than 12 years of age will not complete the psychosocial factors.

NOTE: If you are recruiting participants or receiving, accessing, or using data from a U.S. health care provider, HIPAA review is likely to be required. If you plan to bring identifiable health information from a foreign country to a U.S. covered entity (e.g., lab at the Hopkins SOM), HIPAA may be triggered. Check "yes" to the HIPAA question in the PHIRST application.

V. Study Procedures:

In this section, provide details of your procedures, particularly as they relate to human subjects. If this is a multi-center study, make the role of JHSPH clear. If the JHSPH will serve as **data coordinating center**, indicate in the sections below which procedures JHSPH will not be performing. Additional information regarding data coordinating centers is requested in a later section. If your study will develop in phases, address each item below by phase.

A. Recruitment Process:

1. Describe how you will identify, approach, and inform potential participants about your study. Include details about who will perform these activities and what their qualifications are.

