Participants in the in-depth interviews, focus groups discussions, intervention planning workshops, and pilot will be recruited by trained research assistants from icddr,b through a combination of purposive and convenience sampling strategies. Individuals participating in an in-depth interview may also be invited to participate in a focus group discussion. Government officials and health facility staff and directors will be contacted by phone or approached at their office. Pilot participants will be selected across the geographic catchment area of Dhaka, Bangladesh based on the neighborhoods (wards) where cholera patients are identified. Randomized controlled trial participants will be randomly selected across the geographic catchment area of Dhaka, Bangladesh based on the neighborhoods (wards) where cholera patients are identified. All potential participants will be read a recruitment script, given an opportunity to ask questions, and then screened and consented to participate by trained icddr,b research assistants. Adults in study households will be recruited before children.

2. Address any privacy issues associated with recruitment. If recruitment itself may put potential participants at risk (if study topic is sensitive, or study population may be stigmatized), explain how you will minimize these risks.

We do not anticipate any privacy issues during recruitment.

B. Consent Process:

- 1. Describe the following details about obtaining informed consent from study participants. If a screening process precedes study enrollment, also describe the consent for screening.
 - A. Who will obtain informed consent, and their qualifications:

In-depth interviews, focus group discussions, and intervention planning workshops: A trained icddr,b research assistant who will be conducting the in-depth interviews, focus group discussions, and intervention planning workshops will obtain informed consent from adult participants and assent from children (12-17 years), and informed consent (parental permission) from a parent or guardian.

Pilot trials: A trained icddr,b research assistant will obtain informed consent from adult participants and assent from children (12-17 years), and informed consent from a parent or guardian for our pilot study.

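### No eligibility or selection rule stops two trial households sharing a latrine or cooking area, so a control household could be scored on an intervention household's soap

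*Combined protocol and SAP*

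**What the plan says.** All places are in the combined protocol and SAP.

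- **Allocation.** Aim 2a has 300 households "assigned to one of two study arms (150 households per arm"). The statistical paragraph in III.A compares baseline factors between arms "to determine whether randomization was successful in defining similar groups of households". Both point to the household as the randomised unit, but no section names the unit or describes the procedure.
- **Selection.** Recruitment Process (V.A.1): "Randomized controlled trial participants will be randomly selected across the geographic catchment area of Dhaka, Bangladesh based on the neighborhoods (wards") where cholera cases are found.
- **Eligibility.** The trial list in section IV has four items: an active mobile phone, a child under five, a plan to stay for 12 months, and that participants "must live in an area identified to have cholera patients by the icddr,b surveillance system". None concerns shared facilities, distance between households, or one household per compound.
- **Outcome.** The spot checks in III.A record "the presence of soap in the latrine and cooking areas of the household (within 10 steps"). This is primary outcome (3). The plan does not say how a shared area is scored or whose soap counts.
- **Sizing.** Table 2 gives "Detectable differences for outcomes between intervention and comparison arm for 80% power". It allows for 10% attrition, which leaves 270 of the 300 households. Both soap rows show a 17-point difference, from 31% (cooking area) and 51% (latrine area) in the control arm.

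**The concern.** Soap within a set distance of a latrine or kitchen describes a place. If two enrolled households use the same place and fall in different arms, soap put there by the intervention household scores as present for the control household as well. The control rate rises, the difference shrinks, and the trial may understate an effect that exists. The error runs toward no effect, so it would not produce a false positive.

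The plan has little room to absorb this. The III.A power paragraph says that 300 households is the most the budget allows, so enrolment cannot be raised to make up for dilution. Preventing it at screening is the affordable route.

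**Working it through.** **Inputs from the documents.** 270 households analysed (300 × 0.9), so n = 135 per arm. Control rates p = 0.31 (cooking) and 0.51 (latrine). Difference 0.17. Power 80%.

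**Assumptions.** Two-sided 5% test (the plan states neither alpha nor sidedness) and no continuity correction. Let c be the share of control households scored at the intervention rate because of a shared area. The documents give no value for c.

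**Formula.** With p₁ the control rate, p₂ the intervention rate and p̄ their mean,

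power = Φ{ [ |p₂ − p₁|·√n − 1.96·√(2p̄(1−p̄)) ] / √(p₁(1−p₁) + p₂(1−p₂)) }

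**Step 1: reproduce Table 2.**

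- Cooking, 31% vs 48%: (0.17 × √135 − 1.96 × 0.6913) / 0.6808 = (1.975 − 1.355) / 0.6808 = 0.911, so power is 81.9%.
- Latrine, 51% vs 68%: (1.975 − 1.361) / 0.6837 = 0.899, so power is 81.6%.
- Solving for exactly 80% power gives 16.6 points (cooking) and 16.7 points (latrine). Both round to the stated 17, so Table 2 is confirmed.

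**Step 2: add dilution.** The control rate becomes p + 0.17c, the intervention rate stays at p + 0.17, and the observed difference is 0.17 × (1 − c).

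| c (assumed) | Observed difference (points) | Power, cooking | Power, latrine |
|---|---|---|---|
| 0% | 17.0 | 81.9% | 81.6% |
| 2% | 16.7 | 80.2% | 80.0% |
| 5% | 16.2 | 77.6% | 77.6% |
| 10% | 15.3 | 72.9% | 73.1% |
| 20% | 13.6 | 62.3% | 63.2% |

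Example, latrine at c = 10%: the control rate is 0.51 + 0.017 = 0.527, and (0.153 × √135 − 1.96 × 0.6918) / 0.6833 = 0.617, so power is 73.1%.

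**Step 3: how much sharing each c implies.** Suppose sharing occurs in pairs and each household is randomised 1:1 on its own. About half the pairs then have one household in each arm, and each such pair affects one of the 150 control households. So c × 150 split pairs need 2 × c × 150 sharing pairs, or 4 × c × 150 enrolled households:

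- c = 2%: 12 of 300 households
- c = 5%: 30
- c = 10%: 60
- c = 20%: 120

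Larger sharing groups would need fewer households for the same c.

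**The case against.** The strongest reply is that nothing in the documents shows this happening. No section reports that enrolled households share a latrine or kitchen. A ward is far larger than a group of households using one latrine, and V.A.1 specifies random selection across the Dhaka catchment. The rationale in section II speaks of neighbouring households, but that is not a sampling rule. By Step 3, the higher values of c require a large part of the sample to be sharing. The phrase about areas belonging to the household might also mean private areas only, although it is not defined. Finally, 17 points is what a budget-fixed sample can detect. It is not the expected effect, so power below 80% at 17 points does not show that the trial is underpowered for the effect it will meet. All of this stands. It limits the likelihood and size of the problem, but it does not supply the missing rule.

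A reader might also infer four stronger points, which the documents do not support:

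- **Households in one ward are placed in opposite arms.** The V.A.1 sentence is about selection. Household allocation is a reasonable inference, but stratification or grouping by ward is neither stated nor excluded.
- **Shared records are wrongly treated as independent.** Positive correlation between households in opposite arms lowers the variance of the difference, so ignoring it is conservative. Only same-arm pairs raise the variance. Under independent household randomisation the two roughly offset.
- **Stored water is contaminated in the same way.** The plan measures stored drinking water per household and describes no shared supply.
- **The bias could never be dealt with afterwards.** The screening questionnaire is mentioned but not reproduced, and no baseline form is itemised, so it is unknown whether sharing is recorded.

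**Conclusion.** The concern holds as a gap in the design: as written, the plan lets two enrolled households share a latrine or cooking area and has no scoring rule for that case. If such households fall in different arms, the two soap outcomes are biased toward no effect. The other three rows of Table 2 are not reached by this mechanism.

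The size is unknown. At 2% of control households affected, the small margin above 80% power is used up; at 5% and 10%, power for 17 points is about 78% and 73%. These figures rest on an assumed c, on a two-sided 5% test, and on household randomisation, which is inferred. Under truly scattered selection c may be near zero. This is a cheap improvement worth making, and no figure in Table 2 needs correcting.

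**What to change.** Add a fifth item to the trial eligibility list in section IV: *does not share a latrine, cooking area or compound with a household already enrolled in the trial*. In V.A.1, add that a drawn household failing this item is replaced by the next on the random list. At baseline, record whether the latrine and the cooking area are shared. The same edit can name the household as the randomised unit, if that is what is intended.

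The cost is one screening question, one eligibility sentence and a baseline item. Screening takes slightly longer and a few drawn households are replaced. Sample size does not change. Households that share only with neighbours outside the trial stay eligible unless a neighbour has already been enrolled, so the target population is largely kept. The rule does not stop neighbours in separate compounds copying what they see; it closes only the shared-facility route.
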